# 8.7 Blinding

The study is open-label. However, as stated in the EMA guidelines on investigation of bioavailability and bioequivalence , analysis of the samples should be conducted without information on treatment, therefore the laboratory staff responsible for drug concentration analysis will be blinded to the treatment.

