# 8.8 Prior and Concomitant Medication

Subjects must refrain from using any medication, other than oral contraception, prescribed or over-the-counter (including herbal remedies, St. John's wort [*Hypericum perforatum*]), for 2 weeks before the first administration of IMP and for the duration of the study. Occasional use of paracetamol  $\leq 2$  g/day and/or ibuprofen ( $\leq 1200$  mg/day) is allowed for pain

The administration of concomitant medication will be handled on a case-by-case basis at the discretion of the investigator. If any medication is required during the course of the study, it must immediately be reported to the investigator. Where medication is taken or needs to be taken, a decision whether to continue or discontinue the subject's participation in the study will be based on subject safety, the time of medication administration and the possible influence of the ingested medication on the PK of the IMP and interference with the assay method.

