6.3 Analysis Sets

The **Enrolled set** includes all subjects who provide informed consent irrespective of whether they were randomised or received study treatment.

The **Safety analysis set (SAF)** consists of all subjects who take at least one administration of study treatment. Subjects will be analysed according to the treatment actually taken.

The **Pharmacokinetic (PK) set** will consist of all subjects who complete the study and for whom primary PK variables can be calculated for all treatments.

In case of events such as vomiting, diarrhoea and use of concomitant medication, which could render the plasma concentration time profile unreliable, such subjects may be excluded from the PK population after review of the severity of the event and the start and stop time in relation to dosing. When vomiting occurs within 2x the calculated median t_{max} of the reference (tablet) product, data from all treatments being compared will be excluded from PK and statistical evaluation. Subjects with pre-dose azathioprine concentrations $\geq 5\%$ of C_{max} will be excluded from all statistical PK analysis (including descriptive statistics). The available concentration data of the

above subjects and those who do not complete the study will only be listed, not presented in descriptive statistics or included in PK or formal statistical analysis.

The list of subjects included in the PK will be agreed prior to database lock once all study data is available. The definitions for the enrolled set and SAF are sufficient to determine the subjects included within these analysis sets and so do not require listing and agreeing prior to database lock.

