6.5 Disposition of subjects

The number and percentage of all subjects enrolled, included in the SAF, PK analysis set, who completed the study and prematurely discontinued the study, who completed study treatment and prematurely discontinued study treatment, study duration and treatment duration, will be summarised. The number and percentage of subjects will be summarised by their reasons for withdrawal from the study.

Study duration will be derived as the number of days between first visit and the date of study completion or the date of early study withdrawal. Treatment duration will be derived as the number of days between first administration of study treatment in period 1 and date of study completion or the date of early study withdrawal.

Eligibility for each of the analysis sets along with reasons for exclusion will be listed. Study completion/withdrawal data will be listed.

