6.10 Pharmacokinetics

Summary statistics for PK outputs will be reported using n, arithmetic mean, geometric mean, median, coefficient of variation, standard deviation, minimum and maximum.

For purposes of analysis, the test product is Jayempi 50mg/mL (azathioprine oral suspension) and the reference is Imurek 50mg (oral azathioprine tablet).

Plasma concentrations of azathioprine (both oral and tablet) will be listed and summarised over time. Concentrations below the lower limit of quantification (LLOQ) of 0.2ng/ml will be indicated as below the lower limit of quantification (BLQ). For PK summaries and analyses, BLQ concentrations will be handled as follows:

- All BLQ values in the absorption phase, prior to the first reported concentration, will be substituted by zeros.
- The BLQ values between evaluable concentrations will be substituted by $0.5 \times$ LLOQ, before the calculation of the PK variables.
- Terminal BLQ values will be set to missing.

These measures are taken to prevent an over-estimation of AUC. Values reported as 'NS' (no sample) will be set to "missing".

For the purposes of PK analysis, missing concentrations will be deleted, resulting in an interpolation between the nearest two concentration values. A table reflecting summary statistics per product will be provided for PK variables of azathioprine, including the number of points used to calculate λ_z (λ_z will, however, not be summarised).

A table reflecting summary statistics will be provided for the ratios (%test/reference) of the primary PK variables (C_{max} , AUC_{0-T} and $AUC_{0-\infty}$), for $t_{1/2}$ and for the difference (test – reference) of t_{max} .

Analysis of t_{max} will be done using Wilcoxon's Signed Rank test. The median t_{max} of the test and reference will be tabulated together with the p-value from Wilcoxon's Test.

The test product (azathioprine only) will be compared to the reference product by means of statistical analysis with respect to the primary PK variables (C_{max} , AUC_{0-T} and $AUC_{0-\infty}$) using an analysis of variance (ANOVA) with sequence, subject(sequence), product and period effects after logarithmic transformation of the data. Point estimates and 90% confidence intervals for the "test/reference" geometric mean ratios of these variables will be tabulated.

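### SAP 6.3 settles the discretionary PK-set exclusions at a point when concentrations exist, and nothing keeps those judgements away from them

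*SAP*

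**What the plan says.** SAP 6.3 (Analysis Sets) builds the PK set from two kinds of rule.

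- **Discretionary.** After events such as vomiting, diarrhoea or use of concomitant medication that could make the profile unreliable, "such subjects may be excluded from the PK population after review of the severity of the event" and its timing relative to dosing. Protocol 11.2.1 has the same rule.
- **Fixed.** The subject must complete the study, and the primary PK variables must be calculable for all treatments. "When vomiting occurs within 2x the calculated median" tmax of the reference tablet, exclusion is mandatory. A pre-dose concentration of at least 5% of Cmax also excludes.

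On timing, "The list of subjects included in the PK will be agreed prior to database lock once all study data is available". On data from excluded subjects, SAP 6.3 says that they "will only be listed, not presented in descriptive statistics or included in PK or formal statistical analysis".

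Elsewhere, Protocol 8.7 makes the study open-label and confines blinding to the assay: "therefore the laboratory staff responsible for drug concentration analysis will be blinded to the treatment". SAP 6.5 adds that "Eligibility for each of the analysis sets along with reasons for exclusion will be listed", and SAP 6.10 lists all PK data. The rule in SAP 6.10 that bioequivalence is judged on complete data is written for outliers.

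**The concern.** The PK set carries the primary bioequivalence decision. A judgement about whether an event spoiled a profile is sound when it rests on what happened clinically. It is open to challenge when the person judging can also see the profile, or can work out the subject's own test/reference ratio, because keeping or dropping that subject can then be steered by the answer.

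The SAP gives one point of agreement for the whole list and places it after all data are in. It names no reviewer, does not keep the reviewer from seeing concentrations, and does not put the discretionary decisions first. Excluded subjects are listed but left out of formal analysis, so no planned analysis would show whether discretionary exclusions changed the conclusion. Outliers, by contrast, are analysed both ways.

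**Working it through.** **Step 1. Do concentrations exist when the list is agreed?** Three of the fixed rules in SAP 6.3 need them:

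- Calculable primary variables need the full profiles.
- The vomiting window needs the calculated median tmax of the reference.
- The pre-dose rule needs the pre-dose level and Cmax.

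So the list cannot be completed before assay results are in. This follows from the SAP's own rules.

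**Step 2. Does any text separate the discretionary judgements from those results?**

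- Protocol 8.7 blinds laboratory staff to treatment. It does not cover whoever decides on exclusions.
- Agreement before database lock does not help, because the same sentence requires all data to be available. The documents do not say whether assay results sit in the locked database.
- Protocol 8.8 says "The administration of concomitant medication will be handled on a case-by-case basis at the discretion of the investigator", and Protocol 7.3.3 allows withdrawal for intercurrent illness requiring medication. Both act during conduct. A subject withdrawn before completing also leaves the PK set, so these routes settle some cases early. They do not reach subjects who complete both periods.
- The complete-data rule covers outliers only.

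**Step 3. How much could it matter?** The plan has no figure to reproduce: SAP 3 gives 30 randomised and at least 28 evaluable without formal statistical considerations. The following is an illustration.

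*From the documents:* 28 subjects, a 2x2 crossover, log-scale ANOVA, and a 90% confidence interval within 80.00% to 125.00%.

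*Assumed:* 14 subjects per sequence, within-subject CV 20% to 30%, one variable, true ratio 0.80, and one to four flagged subjects. Any subset of the flagged subjects may be removed, and equivalence is counted if any choice passes.

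*Formulas:* let d be a subject's log(test) minus log(reference).

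- Estimate = (mean d in sequence 1 + mean d in sequence 2)/2.
- SE = sqrt[s²(1/n1 + 1/n2)/4], where s² is the pooled variance of d.
- Interval = estimate ± t(0.95, n1 + n2 − 2) × SE.
- Within-subject SD = sqrt[ln(1 + CV²)], and the SD of d is sqrt(2) times that.

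For CV 20% the within-subject SD is sqrt[ln 1.04] = 0.198. Then SE = 0.198 × sqrt(2) × sqrt[(1/14 + 1/14)/4] = 0.053. For CV 30% the corresponding values are 0.294 and 0.078.

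*Simulated false equivalence, 100,000 trials per cell, flagged subjects unrelated to the results:*

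| Flagged | CV 20% | CV 30% |
|---|---|---|
| 0 | 4.95% | 4.94% |
| 1 | 5.82% | 5.82% |
| 2 | 6.78% | 6.78% |
| 4 | 8.89% | 8.88% |

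At a true ratio of 1.25 the pattern is the same: 5.7% to 5.8% with one flagged subject and 6.6% to 6.7% with two.

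Nobody needs to have seen a confidence interval for this. Dropping a flagged subject whose own ratio is below 0.80 gives nearly the same error: 5.8% with one flagged and 6.6% to 6.8% with two.

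*All three variables required to pass* (Cmax ratio 0.80; both AUC ratios 0.95; correlation 0.98 between the AUCs and 0.6 with Cmax): the error rises from 4.1–4.9% to 4.9–5.7% with one flagged subject and 5.8–6.6% with two.

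**Step 4. What would a choice fixed without results give?**

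- *Event halves exposure in a period that is test or reference at random.* Keeping all or excluding all stays near 5%. Result-driven choice gives about 6.5% to 6.9% with one flagged subject and 8.5% to 9.5% with two.
- *Event halves exposure in the reference period only.* Each such subject shifts the log estimate upward by ln 2/28 = 0.0248. The expected apparent ratio moves from 0.80 to 0.80 × exp(0.0248) = 0.820 with one flagged subject, and to 0.80 × exp(0.0495) = 0.841 with two. Keeping all then gives about 8% to 9% false equivalence with one flagged and 12% to 15% with two. Excluding them gives about 5%.

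The second case shows that clinical exclusion has value in itself. What needs changing is when the decision is made.

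**The case against.** The strongest case against is that the discretion is narrow. It is tied to events that could make the profile unreliable and is judged on severity and timing, so using concentrations would depart from the stated criteria. Reasons for exclusion and all PK data are listed, so an assessor could restore an excluded subject. Part of the concomitant-medication and illness discretion is exercised during conduct through withdrawal. With two single 50 mg doses in healthy volunteers, few flagged subjects are likely, and with one the effect is about one percentage point. A decision made without results is not automatically safer either: keeping subjects whose reference exposure was halved costs more than result-driven choice does when the affected period is random.

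All of this stands and limits the weight of the point. It does not close the gap. The criteria give no threshold, and listings allow the effect to be reconstructed later but do not protect the decision when it is made.

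Two stronger readings are tempting. One is that the PK set will be chosen after seeing ratios or confidence intervals. The documents do not say that these have been produced by then; they imply only that concentrations, and PK quantities derived from them, are available. The other is that false equivalence reaches about 9%. That needs four flagged subjects among 28, and nothing in either document supports that number.

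**Conclusion.** The gap is real and modest. As written, the plan does not ensure that discretionary exclusions of subjects who complete both periods are made without sight of their concentrations. Bias is possible, not shown.

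Under the stated assumptions the error rises from about 5% to about 5.8% with one flagged subject and 6.8% with two, if every choice favours equivalence. These are illustrations, not bounds. CVs, correlations, size of distortion and number of events are all assumed, and the figures are larger if events distort the profile. The statement that choices fixed without results stay near 5% holds when the affected period is random; it fails if reference-period events are kept in.

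The weight is minor to moderate, and the remedy is a cheap improvement.

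**What to change.** Change SAP 6.3 only. Protocol 11.2.1 states no timing, so the change of sequence needs no protocol amendment.

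1. Decide, document and sign off every discretionary exclusion from clinical records before any concentration result is released to those deciding. The reference median tmax will not yet be known, so for each vomiting event record the decision that applies if it proves to fall outside twice that value.
2. After release, apply only the rules already stated: study completion, primary PK variables calculable for all treatments, the vomiting window, and pre-dose concentration of at least 5% of Cmax.
3. Optional, and supportive only because clinical exclusion has value: an analysis restoring discretionary exclusions whose primary PK variables are calculable for both treatments. This needs an exception to the listing-only sentence in SAP 6.3. Protocol 11.2.1 has the same sentence, so the addition should be recorded in SAP 6.19. Protocol 11.2 already allows additional analyses if they are described in the study report.

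Some judgement after results remains. The documents give no acceptance criteria for lambda-z, only a table "including the number of points used to calculate" it, so when AUC0-∞ counts as calculable stays open.

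The cost is SAP wording and one earlier dated sign-off, plus one extra analysis if the option is taken. No extra subjects or procedures are needed.

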6.4 Data presentations

The data will be summarised in tabular form by treatment group ('Oral azathioprine tablet 50mg' and 'Oral azathioprine suspension 10mg/mL' with the following exceptions: disposition of subjects, background and demographic characteristics which will be summarised by treatment sequence ('Oral azathioprine tablet 50mg – Oral azathioprine suspension 10mg/mL' and 'Oral azathioprine suspension 10mg/mL – Oral azathioprine tablet 50mg') and overall subjects ('Overall') treatment group.

Only scheduled post-baseline laboratory, vital signs and ECG values will be tabulated, post-baseline repeat/unscheduled assessments will be disregarded, although they will be listed and in particular all clinically significant values will be noted.

Analysis sets, protocol deviations and eligibility listing will be summarised using the enrolled set, PK outputs will be summarised using the PK set and everything else will be summarised using the SAF.

Listings will be sorted by treatment sequence, subject number and date/time of assessment.

Graphical presentations of the data will also be provided where appropriate.

6.5 Disposition of subjects

The number and percentage of all subjects enrolled, included in the SAF, PK analysis set, who completed the study and prematurely discontinued the study, who completed study treatment and prematurely discontinued study treatment, study duration and treatment duration, will be summarised. The number and percentage of subjects will be summarised by their reasons for withdrawal from the study.

Study duration will be derived as the number of days between first visit and the date of study completion or the date of early study withdrawal. Treatment duration will be derived as the number of days between first administration of study treatment in period 1 and date of study completion or the date of early study withdrawal.

Eligibility for each of the analysis sets along with reasons for exclusion will be listed. Study completion/withdrawal data will be listed.

6.6 Protocol Deviations

Details of all protocol deviations (start and end dates, report type (Full report/Procedural), deviation category, specific details and cause) and subject eligibility will be listed.

6.7 Background and Demographic Characteristics

6.7.1 Demography

Demographic characteristics (age, sex, ethnicity and race), body measurements (height, weight and BMI), average weekly consumption of alcohol and smoking history collected at Screening will be summarised.

Body mass index (BMI) in kg/m² is calculated as

$$\frac{\text{weight in kg}}{(\text{height in cm} / 100)^2}$$

All subject demographic data including informed consent will be listed.

6.7.2 Medical History

Medical history events will be coded using the latest MedDRA dictionary version. The version used will be indicated in the data summaries and listings. The number and percentage of subjects will be presented for ongoing conditions and previous conditions separately by system organ class (SOC), and preferred term (PT), where SOC and PT will be presented in decreasing frequency of the total number of subjects with medical history events. All events will be listed.

6.7.3 Thiopurine Methyltransferase Testing

The date, time and result in mU/L taken at screening will be listed.

6.8 Prior and Concomitant Medications

Medications will be coded using the latest World Health Organization Drug dictionary (WHO Drug) version. The version used will be indicated in the data summaries and listings.

Prior medications are defined as those that started and ended prior to the first administration of study treatment.

Medications that are ongoing at the first administration of study treatment or started after time of first administration will be deemed to be concomitant medications. Concomitant medications will be reported under each period they were concomitant to. For example; a medication starting and ending in period 1 will be assigned to period 1 only. A treatment starting after the first administration of study treatment in period 2 will be assigned to period 2 only. A treatment starting before the end of period 1 and continuing into period 2 will be reported under period 1 and period 2.

For the purposes of concomitant medication, period 1 is defined from day of first administration of study treatment for period 1 to the day before the first administration of study treatment for period 2. If medication dates are incomplete and it is not clear whether the medication was concomitant, it will be assumed to be concomitant.

The number and percentage of subjects taking prior and concomitant medications will be summarised separately by medication class and standardised medication name, where medication class and standardised medication name will be presented in decreasing frequency of the total number of subjects with medications. In summary tables, subjects taking multiple medications in the same medication class or having the same standardised medication recorded multiple times in the study will be counted only once for that specific medication class and standardised medication name.

Medication data will be listed, where concomitant medications will be flagged.

6.9 Study Treatments

A listing will be provided detailing if the subject received any treatment for the period, date and time of administration, the treatment and dose received.

6.10 Pharmacokinetics

Summary statistics for PK outputs will be reported using n, arithmetic mean, geometric mean, median, coefficient of variation, standard deviation, minimum and maximum.

For purposes of analysis, the test product is Jayempi 50mg/mL (azathioprine oral suspension) and the reference is Imurek 50mg (oral azathioprine tablet).

Plasma concentrations of azathioprine (both oral and tablet) will be listed and summarised over time. Concentrations below the lower limit of quantification (LLOQ) of 0.2ng/ml will be indicated as below the lower limit of quantification (BLQ). For PK summaries and analyses, BLQ concentrations will be handled as follows:

- All BLQ values in the absorption phase, prior to the first reported concentration, will be substituted by zeros.
- The BLQ values between evaluable concentrations will be substituted by $0.5 \times$ LLOQ, before the calculation of the PK variables.
- Terminal BLQ values will be set to missing.

These measures are taken to prevent an over-estimation of AUC. Values reported as 'NS' (no sample) will be set to "missing".

For the purposes of PK analysis, missing concentrations will be deleted, resulting in an interpolation between the nearest two concentration values. A table reflecting summary statistics per product will be provided for PK variables of azathioprine, including the number of points used to calculate λ_z (λ_z will, however, not be summarised).

A table reflecting summary statistics will be provided for the ratios (%test/reference) of the primary PK variables (C_{max} , AUC_{0-T} and $AUC_{0-\infty}$), for $t_{1/2}$ and for the difference (test – reference) of t_{max} .

Analysis of t_{max} will be done using Wilcoxon's Signed Rank test. The median t_{max} of the test and reference will be tabulated together with the p-value from Wilcoxon's Test.

The test product (azathioprine only) will be compared to the reference product by means of statistical analysis with respect to the primary PK variables (C_{max} , AUC_{0-T} and $AUC_{0-\infty}$) using an analysis of variance (ANOVA) with sequence, subject(sequence), product and period effects after logarithmic transformation of the data. Point estimates and 90% confidence intervals for the "test/reference" geometric mean ratios of these variables will be tabulated.

Bioequivalence of the test and reference products will be assessed on the basis of the 90% confidence intervals for the geometric mean ratio of the primary PK variables of azathioprine in relation to the conventional bioequivalence range of 80.00% to 125.00%.

In case of outliers present in the data regarding the primary PK parameters, the analyses will be performed on both the complete data and on the data excluding the outliers. Bioequivalence will however be assessed on the complete data.

Plots will be produced for plasma concentration versus actual time as follows:

- Individual subjects plotted together on the same axis per product using a log-linear and linear-linear scales.
- Distinct individual subject plots per product using a log-linear and linear-linear scales.
- Arithmetic and geometric mean plots with both products on same axis using log-linear and linear-linear scales.

All PK data will be listed.

